#### **1.4 Rationale for Dose Selection**

In this trial, patients will be treated with a markedly abbreviated course of the dosing regimen used in the current standard adult HLH protocol. In the standard HLH regimen, etoposide is given at 150 mg/m^2 twice a week for two weeks, followed by weekly therapy, in combination with dexamethasone. In this trial, patients will receive the standard initial two doses of etoposide in the first week (150 mg/m^2 IV x 2) on day 1 and 4 of treatment. Further etoposide therapy will not be given unless the assessment of the patient's subsequent course is that they improved after etoposide treatment but then had recurrent clinical deterioration, at which point further etoposide therapy would be allowed (according to the HLH-94 protocol) after discussion with the investigator.

The rationale for such an abbreviated course of etoposide is three fold. First, the immune hyperactivation in COVID infections may differ from that of patients with classic secondary HLH and may require only a relatively brief period of pharmacologic down-regulation. Second, the development of neutralizing antibodies to COVID are likely to be an important aspect of recovery from this illness and prolonged treatment with etoposide could theoretically blunt such a response. Third, prolonged etoposide therapy will induce more significant myelosuppression in a group of patients who will be susceptible to bacterial super-infection. The proposed two doses of IV etoposide is not expected to cause deep or prolonged myelosuppression.

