## **5.4 Etoposide Expected Toxicities and Management**

Reversible myelotoxicity has been uniformly observed to be the major toxicity for VP-16 and to represent the only clinically significant side effect. Following a single IV injection, peak myelotoxicity occurs at seven to nine days. Following daily injections for five to seven days, myelotoxicity is maximal between 12-16 days from the initiation of therapy. Bone marrow suppression is mainly manifested as granulocytopenia, with thrombocytopenia and anemia occurring to a lesser extent. Gastrointestinal toxicities including transient modest nausea, vomiting, and diarrhea, are common. Other reactions could include aftertaste, rash, pigmentation, pruritis, abdominal pain, constipation, and dysphagia. Occasional alopecia is reported. VP-16 does not produce phlebitis or nephrotoxicity. Rarely anaphylactic-like reactions have been reported, as well as, hypotension. The drug is to be infused over 60 minutes in this study to decrease the potential for hypotension, and the blood pressure and pulse will be monitored during the infusion. Occasionally, chills, fever, peripheral neurotoxicity, stomatitis, hepatotoxicity, transient cortical blindness and radiation recall dermatitis may be a result of VP-16 administration. Stomatitis is usually associated with high dose regimens containing etoposide. The occurrence of acute leukemia has been reported rarely in patients treated with VP-16 in association with other antineoplastic agents. Etoposide can cause fetal harm when administered to a pregnant women. It has been shown to be teratogenic in mice and rats. In females of reproductive potential, etoposide may cause infertility and result in amenorrhea. Premature menopause can occur with etoposide. Recovery of menses and ovulation is related to

age at treatment. Males In male patients, etoposide may result in oligospermia, azoospermia, and permanent loss of fertility. Sperm counts have been reported to return to normal levels in some men, and in some cases, have occurred several years after the end of therapy Secondary leukemias associated with etoposide have been reported. Women of childbearing potential will be advised to avoid becoming pregnant for at least 6 months after the final dose of etoposide. Males with female partners of reproductive potential will be advised to use effective contraception for 4 months after the final etoposide dose.

Safety of etoposide for use by nursing women has not been established.

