## 6. STUDY PROCEDURES & CALENDAR

REQUIRED STUDIES	Screening	Day 1, Day 4 and Day 7 Σ#	Prior to discharge	Day 30*
PHYSICAL				
History & Physical Exam	X	X	X	X
Height, Weight, Body Mass Index, and Body Surface Area	X			
Vital Signs	X	X	X	X
Toxicity Notation	X	X	X	X
Respiratory Status on 8 point scale ^	X	X	X	X
HISTORY				
Concomitant medicines (including COVID therapies, ie hydroxychloroquine, tocilizumab, anakinra) with date of initiation	X			
Smoking status	X			
Comorbidities	X			
Symptoms, including date of symptom onset	X			
LABORATORY				
Beta HCG (for women of childbearing potential)	X			
CBC with Differential +	X	X	X	X
Comprehensive metabolic panel +	X	X	X	X
Lactate Dehydrogenase	X	X	X	X
D-dimer	X	X	X	X
Ferritin	X	X	X	X
C-reactive protein	X	X	X	X
PaO 2 /FIO 2 (P/F) ratio (cohort 2 only)	X	X	X	X
INR (if on warfarin) Ω	X			
ADDITIONAL TESTING				
Electrocardiogram (ECG)	X			

# For subjects randomized to treatment, the data for Day 1 and Day 4 will be collected prior to the etoposide dose (within 24 hours).

\*Information to be obtained as feasible, if patient has been discharged attempts will be made to obtain the information from the patient's primary care provider. If such results are not available, participant will be contacted by the research nurse to assess toxicities.

^ Mortality assessment (included on the 8 point scale) will also be recorded at Day 14 and 60, in addition to Day 30 mentioned above

+ CBC and comprehensive metabolic panel will be measured at least twice weekly during hospitalization. These tests will also be obtained pre-dose 8, 11, 18, and 25 for those patients who require additional etoposide dosing as described above (Section 4.3 and 5.3)

Ω INR to be repeated at least twice weekly for patients on warfarin

Σ Day 1 of treatment for patients randomized to standard of care (SOC) will be considered the day of randomization

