## 7. STATISTICAL CONSIDERATIONS

### 7.1 Sample Size Considerations

This study will be performed with two cohorts 1) severe COVID-19 infection and 2) moderate COVID-19 infection (as defined in inclusion criteria).

The effect of the intervention will be evaluated in each cohort separately. A total of 32 patients will be enrolled in each cohort with a 3:1 allocation ratio (24 Etoposide and 8 control per cohort). Assuming a 30% response rate in the control group for the primary outcome of a 2 point improvement in respiratory status on an 8 point scale at Day 14, we can detect a 50% increase in response in the Etoposide group (80% response rate in the Etoposide group) with a 2-sided  $\alpha$  of 0.05 and 80% power. While this study is not powered to detect a statistically significant difference in outcome, it will provide initial evidence of efficacy if improvement in response is observed.

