Additional safety analyses will be based on the reported adverse events and other clinical information. Safety analyses will be performed in the all-treated (AT) population, consisting of all patients who took at least one dose of study treatment. The safety and tolerability of Etoposide will be evaluated by means of drug-related AE reports, physical examinations, and laboratory safety evaluations and compared between groups using Fisher's exact test. The first 10 patients allocated to the Etoposide group in the ventilated cohort will be evaluated for safety endpoints prior to initiating enrollment in the non-ventilated group.

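### Section 7.2 compares laboratory safety values between arms only by Fisher's exact test, so neutrophil and platelet counts must be grouped first; a comparison on the full scale would use the counts already collected better

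*Combined protocol and SAP*

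**What the plan says.** Section 7.2 says that safety will be judged from drug-related adverse event reports, "physical examinations, and laboratory safety evaluations and compared between groups using Fisher's exact test". It defines no laboratory variable, time window or cut-point. It restricts safety analyses to patients who took at least one dose of study treatment.

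Elsewhere the plan says:

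- Section 5.4 calls myelotoxicity the major toxicity and adds: "Bone marrow suppression is mainly manifested as granulocytopenia, with thrombocytopenia and anemia occurring to a lesser extent".
- Section 1.4 justifies the short course partly by the risk of bacterial super-infection and states: "The proposed two doses of IV etoposide is not expected to cause deep or prolonged myelosuppression".
- The Section 6 calendar has a CBC with differential at screening and on Days 1, 4 and 7, and a footnote says: "CBC and comprehensive metabolic panel will be measured at least twice weekly during hospitalization".
- Section 7.2 tabulates safety parameters by arm with mean, median, SD and range. It compares changes in inflammatory markers by t-test or rank-sum test. Section 2.5 lists white blood cell count among those markers.
- Two ANC limits appear, neither as a safety endpoint: 1000 as an exclusion (Section 3.3) and 500 as a dose hold (Section 5.5).

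**The concern.** Fisher's test needs categories. ANC and platelet counts are continuous, so the planned test can be run only after each patient's count is placed in a group. If counts fall moderately and few patients cross a low line, most of the information is lost at that step. Section 1.4 leads one to expect this pattern.

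The trial has eight controls per cohort and can least afford such a loss on its main expected toxicity. The plan already uses a continuous test for inflammatory markers but not for neutrophils or platelets as safety measures. With no cut fixed in advance, the grouping could also be chosen after the data are seen. A non-significant result could then be given more weight than it can bear.

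**Working it through.** **The plan's own figure.** The only power figure is the 80% for the primary endpoint (Section 7.1: 80% against 30% response, 24 against 8, two-sided 0.05). An unpooled Z test nearly reproduces it: SE = √(0.8×0.2/24 + 0.3×0.7/8) = 0.181; 0.5/0.181 = 2.76; Φ(2.76 − 1.96) = 0.787. Exact power under the planned Fisher test is 67.9%. That is a separate matter. No power figure is given for laboratory safety.

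**Inputs from the documents.** 24 etoposide and 8 control patients per cohort and two-sided α 0.05 (Section 7.1); ANC limits 1000 and 500 (Sections 3.3 and 5.5). I apply 24 against 8 because "The effect of the intervention will be evaluated in each cohort separately".

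**Assumptions.** Log-normal lowest ANC, control median m = 4, 6 or 8 k/uL, SD of log ANC σ = 0.5, 0.7 or 0.9, median halved on etoposide, same σ in both arms.

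**Step 1: what Fisher's test needs.** Enumerating all 25 × 9 tables, the smallest significant etoposide count is:

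- 10/24 (42%) against 0/8 controls, p = 0.035
- 14/24 (58%) against 1/8, p = 0.041
- 17/24 (71%) against 2/8, p = 0.038

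**Step 2: proportion below a cut c.** Controls: pC = Φ[(ln c − ln m)/σ]. Etoposide: pE = Φ[(ln c − ln(m/2))/σ]. Example with m = 6, σ = 0.7, c = 1: pC = Φ(−1.79/0.7) = 0.5% and pE = Φ(−1.10/0.7) = 5.8%. The expected etoposide count is 24 × 0.058 = 1.4, against the 10 needed.

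**Step 3: power.** Fisher: the sum over i, j of Bin(i; 24, pE) × Bin(j; 8, pC) over tables with p ≤ 0.05. Rank-sum: simulation. Fisher entries are ranges over the three medians.

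| σ | Fisher <500 | <1000 | <1500 | <2000 | midway cut | rank-sum |
|---|---|---|---|---|---|---|
| 0.5 | <0.1% | <0.1% | 0–9% | 0–53% | 69% | 88% |
| 0.7 | <0.1% | 0–0.2% | 0–15% | 0.2–32% | 40% | 61% |
| 0.9 | <0.1% | 0–1.5% | 0.1–14% | 1.5–21% | 25% | 41% |

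The midway cut lies between the two medians on the log scale, so its power does not depend on m. It needs both medians to be known. Even there Fisher is behind by 88 − 69 = 19, 61 − 40 = 21 and 41 − 25 = 16 points. Simulation runs differ by about a point, so I quote rank-sum as about 40 to 89%. Its rejection rate with no effect is 4 to 5%.

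**Step 4: a relative cut.** If a patient is scored as having a fall of at least 50% from baseline, and the SD of log change is 0.3 to 0.8, Fisher power is 80% down to 26%. A rank-sum test at the same SDs has 99.9% down to 50%.

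**The case against.** A reader might infer that Fisher's test would almost never detect a halving of neutrophils. The documents do not support that in general. No cut is set, and near-zero power holds only for low absolute cuts. The limits 500 and 1000 are an entry rule and a dose rule, borrowed here for illustration. Fisher's test also allows more than two categories, and Section 9.1 already grades toxicity by CTCAE. This stands, although grading still groups the counts and Fisher's test ignores the order of the grades.

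A reader might also infer that the plan looks at laboratory safety only as yes or no. It does not. Summaries by arm are planned, so a halved median would be visible, and total white count gets a continuous test. This stands in part. The summaries carry no between-arm estimate or CI. The white-count test is not on neutrophils and is framed as improvement. Platelets get no continuous test.

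Nor would a null Fisher result hide something that Section 1.4 denies. That section denies only deep or prolonged myelosuppression, and a low cut addresses depth more directly than a shift in medians does. This stands.

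Conversely, a fall in ANC is not plainly harm. A white count above 15 k/uL counts towards cytokine storm (Section 3.2), and its improvement is a secondary objective. This also stands.

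Finally, patient safety does not rest on this p-value. Blood counts are frequent, Section 5.5 has an ANC hold, and a Medical Monitor reviews events.

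**Conclusion.** The point holds in a conditional form. Fisher's test is the only named between-arm comparison for laboratory safety, and the loss from grouping runs from moderate to nearly total. With a halving on etoposide, Fisher power is at most 1.5% at 500 or 1000/uL and about 25 to 69% at a midway cut, against about 40 to 89% for a rank-sum test. These figures rest on the assumed log-normal distribution, medians and SDs, and on 24 against 8 within a cohort. If both cohorts opened and safety were pooled (48 against 16), Fisher would do better: for example, 24% rather than 1.3% power for 20% below the cut against none.

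A more basic gap comes first. Controls receive standard of care without placebo (Section 4.1), so the all-treated population, read literally, contains no controls. Section 7.2 nevertheless intends a comparison between groups. Changing the test does not settle this; the text must.

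This is a worthwhile, inexpensive improvement to the analysis. It is not evidence that the trial would miss a hazard.

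**What to change.** In Section 7.2:

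1. Keep Fisher's exact test for categorical safety items and graded toxicity.
2. For ANC, platelets and hemoglobin, compare the lowest value over a fixed window, for example Day 4 to Day 14, using only counts on the schedule common to both arms. Section 5.4 puts peak myelotoxicity seven to nine days after a single injection. Counted from the Day 1 and Day 4 doses, that is Days 8 to 10 and 11 to 13, inside this window. Extra unscheduled counts in one arm would lower its minimum by chance, hence the common schedule.
3. Use a rank-sum test, or a linear model on the log count adjusted for the Day 1 value (pre-dose on etoposide, day of randomization in controls). Report a ratio of medians or geometric means with its 95% CI.
4. State that control patients, followed from randomization, belong to this comparison.
5. Keep n (%) below 1000 and below 500/uL by arm, as description bearing on deep myelosuppression.
6. State that a shift in ANC alone will not be labelled toxicity.

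Cost: protocol wording and one extra table, with no new patients, visits or tests. Death or discharge shortens sampling, so the table should show the number of counts per patient in each arm.

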## 8. MEASUREMENT OF EFFECT

### 8.1 Definitions

**Evaluable for toxicity:** All participants who receive at least one dose of study treatment will be evaluable for toxicity from the time of their first treatment.

**Evaluable for objective response:** Only those participants who have received at least one dose of etoposide will be eligible for objective response.

For purposes of data collection, day 1 of patients on the standard of care arm will be the day of randomization.

## 8.2 Response Definitions

8-Point Ordinal Scale:

- 8 - Death;
- 7 - Ventilation in addition to extracorporeal membrane oxygen (ECMO), continuous renal replacement therapy (CRRT), or need for vasopressors (dopamine  $\geq 5$   $\mu$ g/kg/min OR epinephrine  $\geq 0.1$   $\mu$ g/kg/min OR norepinephrine  $\geq 0.1$   $\mu$ g/kg/min);
- 6 - Intubation and mechanical ventilation;
- 5 - Non-invasive mechanical ventilation (NIV) or high-flow oxygen;
- 4 - Hospitalized, requiring oxygen by mask or nasal prongs;
- 3 - Hospitalization without oxygen supplementation;
- 2 - Discharged from hospital either to home with supplemental oxygen OR to inpatient rehabilitation/skilled nursing facility (+/- supplemental oxygen);
- 1 - Discharged to home without supplemental oxygen

When calculating Ventilator Free days, reintubations or re-hospitalizations or death occurring in the first 28 days should result in zero ascribed to time off the ventilator prior to reintubation

When calculating days of hospitalization, re-hospitalization or death occurring in the first 28 days should result in zero ascribed to time out of the hospital prior to readmission.

When determining days of supplemental oxygen use and need for supplemental oxygen, the patient will only be considered to no longer need supplemental oxygen if a room air saturation is  $\geq 90\%$  after five minutes of rest.

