## **2.5 Secondary Objectives**

- Overall Survival at 30 days is a key secondary endpoint.
- Improvement in inflammatory markers associated with cytokine storm (Ferritin, C-Reactive Protein (CRP), d-dimer, white blood cell count)
- Cumulative incidence of grade 3 and 4 adverse events during hospitalization
- Cumulative incidence of serious adverse events during hospitalization
- Duration of hospitalization
- Duration of ventilation
- Ventilator free days (reintubations or death within 28 days will result in zero ascribed time off ventilator prior to reintubation)
- Improvement in oxygenation or paO2/FIO2 ratio

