## 7.2 Statistical Analysis

Tabulations overall, and by treatment group, will be produced for appropriate demographic, baseline, efficacy, and safety parameters, with number and percentages reported for categorical variables and the mean, median, standard deviation, and range for continuous variables. All analyses will be performed at an  $\alpha=0.05$  level using SAS v.4.

Efficacy analyses will be performed in an intention-to-treat (ITT) population consisting of all patients randomized. The difference in ordinal scale improvement rates between treatment arms will be calculated with a 95% confidence interval and formally compared using Fisher's Exact Test. For secondary analysis of the primary endpoint, logistic models individually adjusted for age, diabetes, chronic lung disease/moderate or severe asthma, immunocompromise, liver disease, heart disease/hypertension, smoking and obesity (BMI  $> 40$ ), residence in long-term care facility, will also be examined with odds ratios and 95% confidence intervals reported.

The analysis of secondary time to event endpoints including survival at 30 days, duration of hospitalization, duration of ventilation and ventilator free days, will be compared between treatment arms based on a log-rank test. The median will be estimated with a 95% CI for each treatment arm using the Kaplan-Meier method. Cox proportional Hazards models adjusted individually for age, diabetes, chronic lung disease/moderate or severe asthma, immunocompromise, liver disease, heart disease/hypertension, smoking and obesity (BMI  $> 40$ ), residence in long-term care facility, will also be examined with odds ratios and 95% confidence intervals reported. Changes in inflammatory markers and in oxygenation or  $\text{paO}_2/\text{FIO}_2$  ratio, based on available recorded measurements, will be compared between treatment arms using a two sample t-test, or a Wilcoxon Rank Sum test, as appropriate. Incidence of grade 3 or 4 AEs and serious AEs will be compared using Fisher's Exact test.

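### Ventilator-free days has different zeroing triggers in Sections 2.5 and 8.2, and both leave readmission or death without reintubation ambiguously scored

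*Combined protocol and SAP*

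**What the plan says.** Section 2.5 (Secondary Objectives) lists ventilator-free days with two triggers: "reintubations or death within 28 days will result in zero ascribed time off ventilator prior to reintubation".

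Section 8.2 (Response Definitions) lists three: "When calculating Ventilator Free days, reintubations or re-hospitalizations or death occurring in the first 28 days should result in zero ascribed". It then limits what is zeroed: such events "should result in zero ascribed to time off the ventilator prior to reintubation".

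The sentence after that in Section 8.2 gives the companion rule for hospital days, which has its own anchor: "re-hospitalization or death occurring in the first 28 days should result in zero ascribed to time out of the hospital prior to readmission".

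Section 7.2 (Statistical Analysis) adds no scoring rule. It groups the endpoint with the time-to-event outcomes: "duration of ventilation and ventilator free days, will be compared between treatment arms based on a log-rank test".

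**The concern.** Two current sections define one endpoint, and neither is said to take precedence. They disagree on whether a readmission counts. They also share a gap: the zeroed interval ends at a reintubation, and a patient who dies or is readmitted without one has no such interval. The hospital-days rule is anchored to readmission, but the ventilator rule has no matching anchor for its re-hospitalization trigger.

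Whoever computes the endpoint would have to choose a reading. The trial is open-label (Sections 2.1 and 4.1), so a choice left to the analysis stage could be made with allocation known. All Cohort 1 patients are intubated at entry (Section 3.2), so the endpoint applies to that whole cohort. With 8 controls per cohort (Section 2.3), a few patients scored differently can move the control arm visibly.

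**Working it through.** The plan states no figure for ventilator-free days, so there is none to reproduce. The check scores the same hypothetical patient under each reading.

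**Inputs**
- Triggers and anchor: Sections 2.5 and 8.2.
- Window: W = 28 days. This is taken from the trigger window, because the counting window is not stated separately.
- Arm sizes: 24 etoposide and 8 control per cohort (Section 2.3).
- Extubation at the end of day *e*, readmission on day *r*, death on day *d*: assumed, because the documents give none.

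**Readmission without reintubation, alive and off the ventilator at Day 28**
- Section 2.5: readmission is not a trigger, so the score is W − e.
- Section 8.2, literal: no reintubation occurs, so nothing is zeroed and the score is W − e.
- Section 8.2, reset at readmission: W − r.
- Section 8.2, all time zeroed: 0.

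| e | r | 2.5 | 8.2 literal | 8.2 reset | 8.2 all zeroed |
|---|---|---|---|---|---|
| 5 | 20 | 28 − 5 = 23 | 23 | 28 − 20 = 8 | 0 |
| 3 | 25 | 28 − 3 = 25 | 25 | 28 − 25 = 3 | 0 |
| 10 | 28 | 28 − 10 = 18 | 18 | 28 − 28 = 0 | 0 |
| 14 | 27 | 28 − 14 = 14 | 14 | 28 − 27 = 1 | 0 |

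In the first row the gap between Section 2.5 and the reset reading is 23 − 8 = 15 days. One such patient moves an 8-patient mean by 15/8 = 1.9 days and a 24-patient mean by 15/24 = 0.6 days. These shifts only gauge size, since the plan does not compare means.

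**Death without reintubation**

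The two sections have the same wording on this case and the same two readings.
- Death means zero: 0.
- Literal anchor: d − e. For e = 5 and d = 27 this is 27 − 5 = 22. For e = 3 and d = 10 it is 10 − 3 = 7.

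**When does a gap exceed 20 days?**
- Reset reading: the gap is (W − e) − (W − r) = r − e. With r no later than 28, r − e > 20 needs e ≤ 7. With e at least 1, it needs r ≥ 22.
- Death under the literal anchor: the gap is d − e, with the same limits.
- All time zeroed: the gap is W − e, so e ≤ 7 is enough and the event day does not matter.

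**The case against.** The strongest reply is that a consistent reader meets only one of the two problems. Read literally throughout, Section 8.2 zeroes nothing for a readmission without reintubation, so both sections give 23 in the worked case and do not conflict. Read for its purpose throughout, death scores zero in both sections and the gap of 22 against 0 disappears. The reset at readmission is also an inference: the ventilator sentence does not state it, and it resembles the neighbouring hospital-days rule.

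This is fair, and it limits the size of the point, but it does not remove it. The literal reading reconciles the sections only by making the added word for re-hospitalization do nothing. The purposive reading leaves the sections in disagreement on readmission. The plan does not say which reading to use.

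A reader might infer that the plan sets no value for death. The documents do not support that. Both sections name death within 28 days as a trigger for zero, and zero is the natural reading. The fault is that the trailing phrase about reintubation clouds it.

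A reader might also infer that the conflict between sections routinely puts one patient more than 20 days apart. That does not hold either. Such gaps need the early extubation and timing shown above, and the death gap comes from wording the sections share, not from their disagreement.

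It also stands that no effect on the planned test has been shown, and that the documents give no frequency for these cases.

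**Conclusion.** The definition needs repair. The trigger lists differ on re-hospitalization, and the score for readmission or death without reintubation is ambiguous in both sections. Section 7.2 does not settle it.

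Under the assumed days, the readmission example gives 23 days under Section 2.5 and 8, 0 or 23 under Section 8.2, depending on the reading. Across the worked readmission cases the gap ranges from 0 (literal reading) to 25 (extubated Day 3, all time zeroed). These figures rest on a 28-day counting window and on event days that are not in the documents.

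The consequence is bounded. Ventilator-free days is one of several secondary endpoints, Section 2.5 names 30-day survival as the key one, and the primary analysis is unaffected. The documents do not show which trigger list was intended, so no single corrected score can be given.

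**What to change.** Before analysis, reconcile Sections 2.5 and 8.2 into one identical rule. For example:
- Count days alive and free of invasive ventilation through Day 28.
- Score any death by Day 28 as 0, whether or not the patient was reintubated.
- After a reintubation, count only days after the last extubation.
- State explicitly whether readmission without reintubation changes the score. Readmission does not measure ventilator need, so the default should be no change. The sponsor must confirm which list was intended.

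In Section 7.2, compare arms on this endpoint by Wilcoxon rank-sum instead of log-rank. It is a day count with a floor at zero, not a time to an event, and the section names no event or censoring rule for it. The rank-sum test is already in the plan for inflammatory markers and oxygenation.

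The cost is a small change of wording and analysis. Ventilation status must be known through Day 28 even after discharge. The current definitions already require this, but the plan does not secure it: Section 4.1 describes control follow-up for the primary and secondary objectives as ending at death or discharge, and Section 6 obtains Day 30 information only as feasible. A Day 28 ventilation check for discharged patients should accompany the rule.
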